8.1. Efficacy Assessments

Participants will be recruited by advertisements posted on an internet job board. Screening assessments will occur remotely via phone to evaluate eligibility.

Planned time points for all efficacy assessments are provided in the SoA.

- **Standard assessment.** Participants will be evaluated at baseline, post-intervention and at 1, 3 and 6 months follow up.
 - Baseline assessment will include:
 - *sociodemographic information* (age, race, gender, employment status, annual income, zip code, living situation, health insurance);

8.2. Safety Assessments

- AEs and SAEs will be collected at each contact point with the participant, beginning when the consent form is signed, and throughout the participants participation in the study. Safety events will be reported through an electronic reporting system and evaluated by the Principal Investigator.
- AEs and SAEs that are collected via the text messaging platform will be recorded and evaluated. Specifically, adverse events will be reported and categorized with respect to

their likely relationship to the intervention (i.e. definitely, possibly, not related). Adverse events that might be reasonably related to SMS text messaging include hand or finger pain, or involvement in an accident as a result of sending or receiving a text relating to the study.

- Planned time points for all safety assessments are provided in the SoA.

8.2.1. Physical Examinations

N/A

8.2.2. Vital Signs

N/A

8.2.3. Electrocardiograms

N/A

8.2.4. Clinical Safety Laboratory Assessments

N/A

8.2.5. Pregnancy Testing

Pregnancy will be self-reported throughout the study. No pregnancy tests will be administered.

8.3. Adverse Events (AEs), Serious Adverse Events (SAEs), and Other Safety Reporting

AEs will be reported by the participant. The investigator and any qualified designees are responsible for detecting, documenting, and recording events that meet the definition of an AE or SAE and remain responsible for following up AEs that are serious, considered related to the study intervention or study procedures, or that caused the participant to discontinue the study (see Section 7).

In the unlikely event of an adverse event resulting from participation in this research study, the Click Discovery Lab Standard Operating Procedure will be followed for handling Adverse and Serious Adverse Events. The method of recording, evaluating, and assessing causality of AEs and SAEs and the procedures for completing and transmitting SAE reports are provided in Appendix 3.

[figure not shown]
8.3.1. Time Period and Frequency for Collecting AE and SAE Information

[figure not shown]
All AEs and SAEs will be collected from the signing of the informed consent form (ICF) until the 6 months follow-up as specified in the SoA (Section 1.3).

All SAEs will be recorded and reported to the investigator immediately. Under no circumstance should this exceed 24 hours, as indicated in Appendix 3. The investigator will submit any updated SAE data to Designated Click Medical Monitor within 24 hours of it being available.

8.3.2. Method of Detecting AEs and SAEs

Care will be taken not to introduce bias when detecting AEs and/or SAEs. Open-ended and non-leading verbal questioning of the participant is the preferred method to inquire about AE occurrences.

8.3.3. Follow-up of AEs and SAEs

After the initial AE/SAE report, the investigator is required to proactively follow each participant at subsequent visits/contacts. All SAEs will be followed until resolution, stabilization, the event is otherwise explained, or the participant is lost to follow-up (as defined in Section 7.3). Further information on follow-up procedures is provided in Appendix 3.

[figure not shown]
8.3.4. Regulatory Reporting Requirements for SAEs

[figure not shown]
- Prompt notification by the investigator to the sponsor of an SAE is essential so that legal obligations and ethical responsibilities towards the safety of participants and the safety of a study intervention under clinical investigation are met.
- The sponsor has a legal responsibility to notify both the local regulatory authority and other regulatory agencies about the safety of a study intervention under clinical investigation. The sponsor will comply with country-specific regulatory requirements relating to safety reporting to the regulatory authority, Institutional Review Boards (IRB)/Independent Ethics Committees (IEC), and investigators.
- An investigator who receives an investigator safety report describing an SAE or other specific safety information (e.g., summary or listing of SAEs) from the sponsor will review and file it and will notify the IRB/IEC, if appropriate according to local requirements.

8.3.5. Pregnancy

Pregnancy will be self-reported by the subject. Pregnant females will not be excluded from participation.

- If a pregnancy is reported, the investigator will record pregnancy information on the appropriate form and submit it to the sponsor within 24 hours of learning of the female participant pregnancy.
- While pregnancy itself is not considered to be an AE or SAE, any pregnancy complication or elective termination of a pregnancy for medical reasons will be reported as an AE or SAE.
- Abnormal pregnancy outcomes (e.g., spontaneous abortion, fetal death, stillbirth, congenital anomalies, ectopic pregnancy) are considered SAEs and will be reported as such.
- Any post-study pregnancy-related SAE considered reasonably related to the study intervention by the investigator will be reported to the sponsor as described in Section 8.3.4. While the investigator is not obligated to actively seek this information in former study participants, he or she may learn of an SAE through spontaneous reporting.
- Any female participant who becomes pregnant while participating in the study may continue the study intervention.

[figure not shown]
9. Statistical Considerations

9.1. Statistical Hypotheses

The primary hypothesis is that the EMA and text message intervention will be feasible and well accepted as evaluated by participants completing at least 33% of the surveys and a retention rate $\geq 70\%$.

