4.1. Overall Design

This study is a pilot randomized controlled trial with embedded qualitative research. Eligible participants who complete an informed consent form will be randomized to receive 3 weeks of EMA or 3 weeks of EMA plus the text message intervention for stress management based on a 1:1 allocation using random block sizes of 2.

Eligible participants will sign the consent form online before moving on to complete their baseline assessment. All participants will receive a copy of their signed consent form and will be provided with the research personnel's contact details. Participants who do not complete the baseline survey within 3 days from enrollment will be excluded from the study. Once their baseline is completed, participants will be randomized to receive:

- **Control:** 3 weeks of EMA, consisting of 2 text messages per day delivered at random times during waking hours to prompt participants to complete the survey
- **Intervention:**
 - o 1 week of EMA, consisting of 2 text messages per day delivered at random times during waking hours to prompt participants to complete the survey followed by
 - o 2 additional weeks of EMA in combination with 2 text messages per day with content related to stress management techniques.

At the end of the 3 weeks, participants in both groups will complete a post-intervention survey designed to evaluate participant satisfaction and to gather information for the purposes of improving the content of the text-message intervention. Changes in levels of psychological distress and well-being from baseline will be also evaluated.

At 1, 3 and 6-months post intervention, participants will be contacted via text message to complete a follow up survey. The follow up survey will include the same information collected at baseline with the exclusion of age, race, gender and adverse childhood events.

Participants from either group will be informed that they can withdraw from the study at any time without giving a reason by replying 'STOP' to any of the messages, or by contacting a member of the research team. No further information will be collected from participants who withdraw from the study.

Participants in the control group will be offered the opportunity to receive the intervention after the 6 months follow-up period. No data will be collected from this intervention.

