6.4. Study Intervention Compliance

Subjects will receive study intervention via text messages.

Subjects may remain in the trial, even if they are nonadherent with the digital intervention treatment.

A record of the digital intervention administered to each participant will be maintained. Intervention start and stop dates will also be recorded.

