9.2. Sample Size Determination

Based on an expected small to moderate effects size (17) of the text message intervention for stress management, a sample size of 70 participants (35 participants per arm) will be sufficient to establish feasibility for a 80% powered main trial with an 80% upper confidence limit (18). About 120 participants will be screened to achieve up to 70 enrolled to the study.

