9.3. Analysis Sets

9.4. Statistical Analyses

Primary outcome.

- *Quantitative analysis.* Feasibility of the intervention will be reported as descriptive statistics, focusing on number of individuals who contact the study team with interest in participation; the number of eligible individuals after the initial screening; time taken to recruit the sample; retention rates; the rate of EMA survey completion. Acceptability will be measured as means and standard deviations of responses to each item within the satisfaction questionnaire, and the proportion of participants giving favorable responses.
- *Qualitative analysis.* A codebook and coding guidelines will be developed for analysis of qualitative feedback. Two researchers will code all transcripts using [REDACTED] and add to the codebook as needed. Each researcher will then independently identify main themes. Results will be compared and discussed until an agreement will be reached. Representative samples of feedback from open-ended questions will be also used.

Secondary outcomes.

- *Standard responses.* Sociodemographic responses will be described by mean, standard deviation (SD), and range. Mixed-effects models for repeated measure (MMRM) will be used to examine change in secondary outcomes, with outcomes examined as change in scores between baseline and follow-up. Models will include effects for time, group (control/intervention), group x time interactions and baseline values of the outcome variable (to control regression to the mean) and other potential confounders. Per Protocol analysis will be performed. The per protocol population will include all randomized participants excluding those who had protocol violations. A significance level of 0.05 will be used. All analyses will be performed using [REDACTED]

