- *EMA responses.* Variability in momentary responses will be described by each participant's mean, SD, and range of mean square successive difference (34), which is a measure of variability that accounts for the temporal order of responses. Analyses on momentary responses will be conducted using Multilevel Modelling (35) because of the hierarchical structure of the data (level 1 = measurement time, level 2 = measurement day, level 3 = participant) and the aptness for dealing with varying time intervals between assessments and missing data. For depicting systematic (i.e. changing with time) or unsystematic (i.e. symptom variability) inter- and intraindividual variations in symptom severity and coping strategies, intraclass correlation coefficients (ICCs) will be used, while associations of symptomatology, coping efficacy and HCC will be analyzed using multilevel correlation and regression analyses.

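### The 33% survey criterion and the single EMA completion rate pool the EMA-only first week with the two stress-text weeks, so a fall below 33% after the stress texts start could go unseen

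*Combined protocol and SAP*

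**What the plan says.** Section 4.1 gives the intervention arm two phases. The first is "1 week of EMA, consisting of 2 text messages per day". The second is "2 additional weeks of EMA in combination with 2 text messages per day with content related to stress management techniques". The control arm has EMA alone for all three weeks. The Schedule of Assessments places the three weeks on Days 5-25, so the first phase is Days 5-11 and the second is Days 12-25.

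The primary hypothesis in section 9.1 is that the EMA and text programme is feasible and well accepted, "evaluated by participants completing at least 33% of the surveys" together with retention of at least 70%. Among the descriptive feasibility results, section 9.4 lists "the rate of EMA survey completion". The outcome tables in sections 1.1 and 3 count EMA response across the whole three weeks. None of these places splits completion at the point where the stress texts begin.

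Section 9.2 says that the sample "will be sufficient to establish feasibility for a 80% powered main trial".

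**The concern.** When the stress texts start, an intervention participant goes from 2 messages a day to 4, if EMA prompting continues at its week-1 pace. Whether people keep answering under that load is a central feasibility question for the combined programme, and week 1 carries no information on it. One figure over three weeks lets good responding before the stress texts offset poor responding after them.

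At stake is what the pilot can tell the planners of a main trial. A favourable statement about the combined programme could rest largely on a week in which participants received only half of it. The control arm answers EMA on the same calendar of days and could show how much decline is ordinary EMA fatigue, but the plan does not ask for that comparison.

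**Working it through.** The 33% has no stated derivation, so there is no figure of the plan's to reproduce. The check is a count.

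**Inputs**
- 2 EMA prompts a day in week 1 (section 4.1). For Days 12-25 the same pace is assumed; it is implied but not restated.
- Threshold 33% (section 9.1).
- 35 participants per arm (section 5).
- Completion rates and SDs below are assumed, because the documents give none.

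**Survey counts**
- Days 5-11: 7 × 2 = 14.
- Days 12-25: 14 × 2 = 28.
- Total: 42, of which 14/42 = 33.3% precede any stress text.

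**Read per participant**
- 0.33 × 42 = 13.86, so 14 surveys are needed (13/42 = 31.0% fails; 14/42 = 33.3% passes).
- After 10 of 14 in week 1: 14 − 10 = 4, and 4/28 = 14.3%.
- After 7 of 14: 14 − 7 = 7, and 7/28 = 25%.

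**Read as an arm rate**

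Let p1 be the rate on Days 5-11 and p2 the rate on Days 12-25. The pooled rate is (p1 + 2·p2)/3. It reaches 0.33 when p2 ≥ (0.99 − p1)/2.

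| Assumed p1 | Lowest p2 that still meets 33% pooled |
|---|---|
| 60% | 19.5% |
| 80% | 9.5% |
| 90% | 4.5% |

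Example: p1 = 80% and p2 = 20% give (0.80 + 0.40)/3 = 40% pooled. The criterion is met although Days 12-25 are well under 33%. By contrast, p1 = 80% and p2 = 40% give (0.80 + 0.80)/3 = 53%, and both figures clear 33%. So when week 1 is at or above 33%, the pooled and later-period results disagree only if p2 is below 33%.

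**Sensitivity to what counts as a survey**

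Section 9.1 does not define the surveys. Baseline is done by everyone randomised, because "Participants who do not complete the baseline survey within 3 days from enrollment will be excluded from the study". After 10 EMA surveys in week 1:
- Adding baseline and post-intervention: 42 + 2 = 44; 0.33 × 44 = 14.52, so 15 needed. EMA surveys still required: 15 − 10 − 2 = 3 if both are done, 15 − 10 − 1 = 4 if only baseline is done.
- Adding the three follow-ups as well: 42 + 5 = 47; 0.33 × 47 = 15.51, so 16 needed. Still required: 16 − 10 − 5 = 1 if all five are done, 16 − 10 − 1 = 5 if only baseline is done.

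Across these readings 1 to 5 of 28 are needed, so the conclusion does not depend on the denominator.

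**Precision of a split by arm**

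The 95% half-width for the between-arm difference in change is 1.96 × SD × √(2/35). For an SD of individual change of 20, 25 or 30 percentage points this is 9.4, 11.7 or 14.1 points.

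**The case against.** The strongest reply is that pooling is the plan's stated choice. The outcome is defined over three weeks, the intervention is described as lasting three weeks, and EMA alone is itself under study, so week 1 is valid evidence. This stands, and it is why the 3-week criterion should not be removed.

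A reader might go further and conclude that 9.1 should be replaced, in the intervention arm, by at least 10 of 28 surveys on Days 12-25 (0.33 × 28 = 9.24). The documents do not support that. Section 9.1 does not say whether 33% applies to each participant or to the arm, and it sets no share of participants who must reach it. A per-participant rule would therefore trigger no stated decision, and it would give one arm a different window from the other.

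Other safeguards help in part. Section 7.3 requires contact after two consecutive missed days. Someone answering 4 of 28 surveys is silent on at least 10 of 14 days; four active days split these into at most five gaps, so some gap lasts two days or more and contact must follow. But only the unreachable are then treated as withdrawn, section 7.2 expects withdrawal to be uncommon, and section 6.4 says: "Subjects may remain in the trial, even if they are nonadherent with the digital intervention treatment". Satisfaction items cover the stress texts, but they record opinion at the end and not continued responding. The multilevel models in 9.4 ("level 1 = measurement time, level 2 = measurement day, level 3 = participant") analyse the content of momentary answers, not whether they were given.

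Finally, parts of sections 8.1 and 9.3 are not visible, and a definition of the surveys may stand there.

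**Conclusion.** The point holds as a reporting gap with a nearly free remedy. The pooled figure can meet 33% while Days 12-25 are far below it: 4 of 28 (14.3%) suffices after 10 of 14, and 80% falling to 20% reads as 40%. This assumes two EMA surveys a day throughout and, for the arm example, rates that the documents do not give. If later responding stays at 33% or more after a week 1 that also reaches 33%, pooling changes no conclusion.

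Three stronger inferences should be resisted:
- That participants could commonly pass on week 1 alone. Under the EMA-only reading this needs 14 of 14, an edge case.
- That 9.1 is a formal progression rule for the main trial. No visible text makes it one; the effect is on how feasibility is described.
- That low completion on Days 12-25 would show rejection of the stress texts. EMA completion measures continued responding, not reading of texts that participants are told not to answer (section 6.2).

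**What to change.** In 9.4, report EMA completion by arm for Days 5-11 and Days 12-25, with the change between periods in each arm and the between-arm difference in change with a 95% CI. Label this descriptive: a half-width of about 9 to 14 points (assumed SD 20 to 30 points) gives an indication of whether a fall exceeds ordinary fatigue, not a test of it. Keep the pooled 3-week rate.

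In 9.1, keep the 3-week criterion and add that the intervention arm's Days 12-25 completion rate will be stated against the same 33% beside it when concluding on the EMA plus text programme. Say how prompts falling after withdrawal are counted.

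The schedule, the retention criterion and the satisfaction measures stay as they are. The cost is about two sentences and one extra table, from data already recorded by day. The downside is that the feasibility conclusion may be slightly less favourable.

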9.2. Sample Size Determination

Based on an expected small to moderate effects size (17) of the text message intervention for stress management, a sample size of 70 participants (35 participants per arm) will be sufficient to establish feasibility for a 80% powered main trial with an 80% upper confidence limit (18). About 120 participants will be screened to achieve up to 70 enrolled to the study.

9.3. Analysis Sets

9.4. Statistical Analyses

Primary outcome.

- *Quantitative analysis.* Feasibility of the intervention will be reported as descriptive statistics, focusing on number of individuals who contact the study team with interest in participation; the number of eligible individuals after the initial screening; time taken to recruit the sample; retention rates; the rate of EMA survey completion. Acceptability will be measured as means and standard deviations of responses to each item within the satisfaction questionnaire, and the proportion of participants giving favorable responses.
- *Qualitative analysis.* A codebook and coding guidelines will be developed for analysis of qualitative feedback. Two researchers will code all transcripts using [REDACTED] and add to the codebook as needed. Each researcher will then independently identify main themes. Results will be compared and discussed until an agreement will be reached. Representative samples of feedback from open-ended questions will be also used.

Secondary outcomes.

- *Standard responses.* Sociodemographic responses will be described by mean, standard deviation (SD), and range. Mixed-effects models for repeated measure (MMRM) will be used to examine change in secondary outcomes, with outcomes examined as change in scores between baseline and follow-up. Models will include effects for time, group (control/intervention), group x time interactions and baseline values of the outcome variable (to control regression to the mean) and other potential confounders. Per Protocol analysis will be performed. The per protocol population will include all randomized participants excluding those who had protocol violations. A significance level of 0.05 will be used. All analyses will be performed using [REDACTED]
- *EMA responses.* Variability in momentary responses will be described by each participant's mean, SD, and range of mean square successive difference (34), which is a measure of variability that accounts for the temporal order of responses. Analyses on momentary responses will be conducted using Multilevel Modelling (35) because of the hierarchical structure of the data (level 1 = measurement time, level 2 = measurement day, level 3 = participant) and the aptness for dealing with varying time intervals between assessments and missing data. For depicting systematic (i.e. changing with time) or unsystematic (i.e. symptom variability) inter- and intraindividual variations in symptom severity and coping strategies, intraclass correlation coefficients (ICCs) will be used, while associations of symptomatology, coping efficacy and HCC will be analyzed using multilevel correlation and regression analyses.

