4.3. End of Study Definition

The end of trial date is defined as the date at which all subjects have completed all activities shown in the Schedule of Assessments, all data has been entered, all data queries have been resolved, and the database has been locked.

5. Study Population

70 participants will be randomized to control (n=35) or intervention group (n=35)

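### Section 9.4 describes sociodemographic responses by mean, SD and range, but most of the items listed in section 8.1 are categorical and need counts and percentages by arm

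*Combined protocol and SAP*

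**What the plan says.** The summary rule is in section 9.4, under the standard responses of the secondary outcomes: "Sociodemographic responses will be described by mean, standard deviation (SD), and range". It makes no distinction by type of variable and does not say that the summary is by arm.

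Section 8.1 gives the items collected at baseline in one complete parenthesis: "age, race, gender, employment status, annual income, zip code, living situation, health insurance". The response options are not shown.

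The study population statement in section 5 fixes the size: "70 participants will be randomized to control (n=35) or intervention group (n=35"). Section 4.1 describes the randomisation as "based on a 1:1 allocation using random block sizes of 2" and names no stratification factor. Section 9.4 also says that the mixed model will include "baseline values of the outcome variable (to control regression to the mean) and other potential confounders", without naming those confounders.

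The plan does use proportions elsewhere. For acceptability, section 9.4 asks for "the proportion of participants giving favorable responses". No visible text plans counts or percentages for the sociodemographic items.

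**The concern.** Mean, SD and range suit a measured quantity such as age. Applied to race, employment status or zip code, they summarise the numbers that happen to label the categories. Change the labels and the result changes, though nobody in the sample has. Followed literally, the rule produces a table that cannot be read for most of the listed items.

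What is at stake is the description of who took part and how alike the two arms were. Randomisation is unstratified with 35 per arm, so chance differences in these characteristics are plausible. Recruitment is through an internet job board (section 5.5), so employment status and health insurance are among the things a reader would want to see. For multi-level items, the stated summary would not show them in usable form and could give matching figures for arms that differ.

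**Working it through.** The plan attaches no figure to this rule, so there is nothing to reproduce. The check has three parts.

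**1. Count the items by type (list in section 8.1).**

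- Numeric: age (1).
- Numeric or banded, format not given: annual income (1).
- Categorical: race, gender, employment status, zip code, living situation, health insurance (6).

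The rule misfits the type of 6/8 = 75% of the items, or 7/8 = 87.5% if income is banded.

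**2. Can equal mean, SD and range hide different arms?** Inputs: n = 35 per arm (section 5); a five-level nominal item coded 1 to 5 (my assumption, since response options are not shown). With n_k participants in category k, let S1 = Σ k·n_k and S2 = Σ k²·n_k. Then mean = S1/35 and SD = √[(S2 − S1²/35)/34].

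| | Arm A | Arm B |
|---|---|---|
| Counts, codes 1 to 5 | 1, 0, 24, 0, 10 | 2, 6, 0, 26, 1 |
| S1 | 1 + 72 + 50 = 123 | 2 + 12 + 104 + 5 = 123 |
| S2 | 1 + 216 + 250 = 467 | 2 + 24 + 416 + 25 = 467 |
| Mean | 123/35 = 3.51 | 3.51 |
| SD | √[(467 − 432.26)/34] = 1.01 | 1.01 |
| Range | 1 to 5 | 1 to 5 |
| Percentages | 2.9, 0, 68.6, 0, 28.6 | 5.7, 17.1, 0, 74.3, 2.9 |

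The three planned statistics agree exactly. The counts differ by 1 + 6 + 24 + 26 + 9 = 66, so 66/2 = 33 of 35 participants would have to change category for the arms to match. The percentages show this at once. The pair came from a search over all distributions for the largest hidden difference, so it is an extreme case and not a typical one.

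**3. Does the result depend on the coding?** Take illustrative counts (20, 8, 4, 2, 1) in one arm.

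- Codes 1, 2, 3, 4, 5: mean = 61/35 = 1.74, SD 1.07.
- The same people with codes 3, 1, 5, 2, 4: mean = 96/35 = 2.74, SD 1.20.

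**Exception.** For a two-level item coded 0/1, the mean is the proportion. With 14 of 35 in one arm and 23 of 35 in the other, the means are 0.400 and 0.657, and the imbalance shows.

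**The case against.** The best defence is that the sentence is loose shorthand: nobody would report a mean zip code, and any standard baseline table would give counts. That may well happen, but it would depart from the written plan. The same section names proportions where it wants them, so their absence here cannot simply be read in. This part of the defence does not remove the point.

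Other parts stand and limit it. A reader might infer that the planned summary can never show imbalance. The documents do not support that. A two-level item coded 0/1 shows it through the mean, and gender, living situation or health insurance may have been asked that way. With three levels and no missing answers, n, mean and SD give three equations for three counts, so exact masking needs at least four levels. Simple contrasts are also exposed. If one arm splits 17/18 between codes 1 and 3 and the other lies wholly in code 2, the means are 71/35 = 2.03 and 2, but the SDs are about 1.01 and 0 and the ranges are 1 to 3 and 2 to 2.

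A reader might also infer that this sentence is the only description of who was studied. It is not. There are eligibility criteria with score cut-offs (sections 5.1 and 5.2), a screening log with reasons for failure (section 8), the numbers interested and eligible (section 9.4), and baseline values of the outcomes. Finally, a comparison of retained with lost participants might be useful, but the plan never proposes one, and its absence does not come from this sentence.

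**Conclusion.** The point holds as a minor one. The rule in section 9.4 does not fit most of the items in section 8.1: six of eight by type, seven if income is banded. For nominal items with several levels, it yields values that depend on the coding and can conceal even a large difference between arms, as the five-level example shows. Both the number of levels and the codes in that example are assumptions. How many items would in fact be unreadable depends on response options that the documents do not give.

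The effect stops at the description of the sample and of arm comparability. A reader might infer that the study's conclusions are at risk, but the documents do not support this. The primary hypothesis in section 9.1 rests on survey completion and retention, which use no sociodemographic summary. The sample size in section 9.2 does not depend on it. The mixed model is fitted to the data and not to the descriptive table, and it already includes the baseline value of each outcome. The most one can say is that clear baseline counts would help a reader judge the unnamed confounders.

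**What to change.** Replace the sentence in section 9.4 with:

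> Age, and income if recorded as an amount, will be described by mean, SD and range; categorical sociodemographic items will be described by counts and percentages; all by randomised arm.

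The cost is one sentence and a standard baseline table. It needs no new data and no change to any other analysis. In the example above, the hidden difference would then appear directly, for instance as 68.6% against 0% in the third category and 0% against 74.3% in the fourth.
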